Efficacy evaluations: SALT, PGA, and Patient global assessment will be performed at every visit. PGA and patient evaluations will be based on similar 100mm visual analog scales. Patient quality of life assessments, performed at baseline, weeks 12, 24, 36, and 48, will be based on changes in the Dermatology Life Quality Index DLQI – adapted for hair loss, or the Dermatology Quality of Life Scales. Blood draws for safety assessments and immunology will be drawn at weeks 4, 12, 24 and 28(if needed for safety labs). Scalp biopsies for immunologic parameters will be obtained at baseline, and at one time point between weeks 4 and 20. Additional biopsies and blood draws may be obtained as clinically indicated. Since the timeline to regrowth may vary from subject to subject, unscheduled biopsies and blood draws will insure that tissue and blood samples are obtained at optimal timepoints to evaluate the changes occurring at the onset of growth or in the event of any unexpected clinical change. In addition, areas that are resistant to treatment may be biopsied to determine the cellular and immunologic differences of those areas compared to areas that are responding to treatment.

The patient will be given the option to agree to, or decline, the additional biopsies and blood draws.

Standardized photographs of the subject's scalp will be taken at Baseline, Week 4, 8, 12, 16, 20, 24, 36 and 48 and will be used to support determination of percent hair regrowth. Photography will consist of a high resolution digital camera mounted on a stereotactic arm. Patients will be positioned using a fixed guide after which photographs of the entire scalp will be taken at standardized locations and at a fixed distance. At a minimum, photographs of the crown, right and left lateral scalp and posterior scalp (views consistent with those used in the SALT measurement) will be taken.

Visit Schedule and Assessments

Screening assessments and all scheduled study visits are outlined in the Table of Study Assessments (please see below).

Informed consent

Written informed consent will be obtained from all patients for this study by the principal investigator or his/her designee prior to any protocol-specific procedures. The study will be conducted in accordance with the Food and Drug Administration (FDA) approved revision of the Declaration of Helsinki, current FDA regulations, and International Conference on Harmonization (ICH) guidelines.

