An unscheduled visit can occur at any time during the study. A source document must be maintained for these unscheduled visits. The date for the visit and any data generated must be recorded on the appropriate CRF. At treatment discontinuation/early termination subjects will undergo off study evaluations per the Schedule of Assessments.

Telephone contact/retention

Patients will be contacted on a biweekly basis throughout the duration of the study to ascertain the occurrence of adverse events as well as to assess the status of hair growth or loss. Any concerns or questions the patient may have will also be addressed.

Assessment of efficacy

The primary efficacy endpoint of this intention to treat trial in AAP will be the proportion of responders in the treated compared to the control group after 6 months of treatment, with response defined as 50% or greater hair re-growth from baseline as assessed by SALT (Severity of Alopecia Tool) (Olsen et al. 2004) score at week 24. This is a relatively strict definition for defining responders and non-responders and was chosen based on consensus of clinicians and AA experts that 50% reduction in SALT score represents clinically

meaningful response and to minimize responses in the “vehicle” arm, in which fewer than 10% are expected to achieve this magnitude of hair regrowth spontaneously. This outcome was also used in two recent RCT trials (Strober et al. 2009 and Price et al. 2008) evaluating therapies for AA.

As secondary endpoints, efficacy will be measured by changes in hair re-growth as a continuous variable as determined by physical exam and Canfield photography, as well as patient and physician global evaluation scores. To assess the durability of responses, patients who achieve 50% reduction in baseline SALT score will continue to be followed for an additional 6 months off treatment.

Secondary efficacy outcomes in detail:

1. Percent hair regrowth from baseline determined by SALT measurements following 4, 8, 12, 20 and 24 weeks of treatment and during the observational phase at weeks 28, 32, 36, 40, 44 and 48.
2. Comparison of the proportion of responders in each group, with response defined as 50% change in SALT score (50% regrowth) from baseline, at weeks 12, 24, 36 and 48.
3. Comparison of the proportion of subjects in each group attaining global overall improvement SALT score of A5 (100% coverage) supported by </= SALT 25 at weeks 12, 24, 36 and 48.

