As secondary endpoints, efficacy will be measured by changes in hair re-growth as a continuous variable as determined by physical exam and Canfield photography, as well as patient and physician global evaluation scores. To assess the durability of responses, patients who achieve 50% reduction in baseline SALT score will continue to be followed for an additional 6 months off treatment.

Secondary efficacy outcomes will include:

1. Percent hair regrowth from baseline determined by SALT measurements following 12, 24 weeks of treatment and at weeks 36 and 48 following discontinuation of treatment (Price et al Efalizumab study)
2. Comparison of the proportion of responders in each group, with response defined as 50% change in SALT score (50% regrowth) from baseline, at weeks 12, 36 and 48.
3. Comparison of the proportion of subjects in each group attaining global overall improvement SALT score of A5 (100% coverage) supported by </= SALT 25 at weeks 12, 24, 36 and 48.
4. Change in PGA (Physician global assessment) based on evaluation of live evaluations and standardized photographs between baseline, week 12, 24, 36 and 48
5. Change in patient global assessment (100mm Visual analogue scale) between baseline, Week 12, 24, 36 and 48
6. Change in patient quality of life assessment (DLQI or DQLS) from baseline to weeks 12, 24, 36 and 48. (Finlay and Khan 1994).
7. Frequency of occurrence and timing of relapse (as defined above) in responders followed for 6 months off therapy.

Safety and tolerability measures:

Incidence and severity of adverse effects (AEs) including the presence and degree of skin atrophy.

Incidence of treatment-emergent laboratory abnormalities.

Sample size

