Power analysis is based on a chi-squared test of proportions of responders in the 4 study groups, where response is defined as 50% reduction in SALT score. Effect size is quantified in terms of Cohen's w , a function of the response rates in the fourgroups (15). A minimal treatment effect size of 40% (Cohen's $w = 0.4$) i.e. a 50% response rate for active drug (IL TAC 2.5mg/ml, 5mg/ml or 10mg/ml) versus a presumed spontaneous remission response rate of 10% for patients receiving inactive IL saline, would be considered clinically meaningful in this study. To achieve 80% power to detect the desired effect size of 40% with a usual 5% level of significance (alpha), we would require approximately 17 subjects per arm (68 subjects in total). With this sample size, an effect size of 50% (Cohen's $w = 0.5$, "large" effect) would ensure approximately 95% power. Our postulated effect size for IL TAC is based on impressions due to clinical use of IL TAC in AA, however an explicit aim of this pilot study is to objectively and more precisely quantify the actual treatment effect of the various doses of IL TAC versus saline placebo.

Data Analysis Plan

The primary analysis will be a comparison of response rates in the 4 study groups, using a chi-squared test of proportions. If the 4-group comparison is significant, we will compare the efficacy and safety profiles of the three doses of intralesional triamcinolone head to head. For secondary outcomes that are binary (response/non-response), we will follow the same strategy. For secondary outcomes that are continuous (e.g. change in SALT measurement or PGA), we will conduct 4-group ANOVA tests, followed by pairwise

comparisons, if necessary. In both cases, Bonferroni correction will be made to adjust for multiple testing. To assess safety, we will summarize and test the incidence rates of adverse events across groups.

If possible, we will attempt to stratify the patients based on baseline degree of hair loss e.g. 0-25% vs. 26-50% hair loss in order to assess if response is correlated with degree of hair loss present at baseline. (Olsen E. Investigative guidelines for alopecia areata.

Dermatologic therapy 24, 2011 311-319

All outcomes will be analyzed on the intent to treat (ITT) basis.

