Each year the Dermatology Department at CUMC sees 600 AA visits each year. Of these we expect roughly 20 to 30% to be eligible for this study of mild to moderate patch type alopecia. We also have a database of almost 400 patients evaluated at CUMC as part of the alopecia areata registry who have expressed an interest in being contacted for clinical trials in alopecia areata. In addition, we hope to have information regarding the study posted on the website for the National Alopecia Areata Foundation (NAAF) the largest AA patient advocacy organization. We expect to complete accrual of 68 patients within the 1 to 2 year study period (38 patients at CUMC and 30 at the University of Minnesota). This time frame will enable 6 months on treatment and 6 months follow-up off drug (for patients who qualify) and completion of the clinical correlative portion of the study

Assessment of Safety

Safety precautions such as the use of highly experienced investigators, frequent visits, and close monitoring of clinical and laboratory findings have been implemented in the protocol and are specified in the Schedule of Assessments. Hematology and chemistry measurements, including WBC count, platelet and absolute neutrophil counts, urinalysis and hepatic panel may be obtained at screening and at other time points if deemed necessary by the investigator.

All physical examination findings, vital sign abnormalities, and clinical laboratory abnormalities, will be captured as AEs when deemed medically significant by the investigator. A qualified physician associated with the study will be available to assess clinical signs and symptoms that may be indicative of an adverse event. Safety will be assessed by

summarizing the incidence and type of AEs. The proportion of patients who discontinued treatment will be summarized.

Methods and Timing of Safety Assessments

Adverse Event Reporting

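### Continuous secondary outcomes are planned as 4-group ANOVAs with no rule for missing values, so earlier visits do not inform the week-24 comparison, which is open to bias of unknown direction

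*Combined protocol and SAP*

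**What the plan says.** **Method.** The Data Analysis Plan states: "For secondary outcomes that are continuous (e.g. change in SALT measurement or PGA), we will conduct 4-group ANOVA tests". Pairwise comparisons follow if needed, with Bonferroni correction. No repeated-measures or mixed model is named anywhere in the document.

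**Population.** The same section states: "All outcomes will be analyzed on the intent to treat (ITT) basis". It does not say how a missing value enters that analysis. There is no imputation rule, no last-value rule and no sensitivity analysis.

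**Measurement.** Under Efficacy evaluations: "SALT, PGA, and Patient global assessment will be performed at every visit". The Study Schedule of Assessments confirms weeks 4, 8, 12, 16, 20 and 24 on treatment. Quality of life is sparser: "Patient quality of life assessments, performed at baseline, weeks 12, 24, 36, and 48".

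**Endpoints.** The list under Assessment of efficacy has "Percent hair regrowth from baseline determined by SALT measurements following 4, 8, 12, 20 and 24 weeks of treatment", plus the observation visits. The list under Study outcomes has "Percent hair regrowth from baseline determined by SALT measurements following 12, 24 weeks of treatment and at weeks 36 and 48". Week 16 is in neither list. PGA, patient global assessment and quality of life are defined as changes to weeks 12, 24, 36 and 48.

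**Early leavers.** Under Unscheduled Visits: "At treatment discontinuation/early termination subjects will undergo off study evaluations per the Schedule of Assessments". The Early Termination list includes SALT, PGA, patient global assessment and quality of life, but nothing says how these values are analysed.

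**Dropout.** Under Assessment of Safety: "The proportion of patients who discontinued treatment will be summarized". No rate is anticipated, and the Sample size section makes no allowance for dropout.

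**The concern.** The endpoints are changes to named weeks and the only method is a 4-group ANOVA, so the natural reading is one ANOVA per outcome and week. Such an analysis at week 24 uses only patients who have a week-24 value. A patient who leaves after week 16 has values at weeks 4, 8, 12 and 16, and none of them contributes. With 17 patients per arm, each leaver is 1/17 = 5.9% of an arm.

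Two things are at stake. Information already collected is discarded in a small trial whose stated purpose includes quantifying the effect of each dose. In addition, if leaving is related to regrowth and the relation differs between arms, the patients who remain no longer form randomised groups, and the week-24 difference is biased.

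**Working it through.** **1. The plan's own figure.** The documents give no SD, effect or power for a continuous outcome. The only design figure belongs to the binary primary endpoint: 68 patients, a 3-df chi-squared test, alpha 0.05. With noncentrality N × w², w = 0.4 gives 68 × 0.16 = 10.88 and power 79.9%. With w = 0.5 it is 68 × 0.25 = 17 and power 94.8%. Both match the stated 80% and 95% for w as stated. They say nothing about the present point.

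**2. Direction of the error.** Everything here is assumed, not taken from the documents: mean week-24 regrowth 45% on one active arm and 10% on saline, SD 40, adjacent-visit correlation 0.8, and dropout depending on regrowth seen at the previous visit. The simulation used 200,000 patients per arm. The full-data difference is 34.8 points.

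| Who leaves active | Who leaves saline | Dropout active / saline | Week-24 difference, available cases | Error |
|---|---|---|---|---|
| Unrelated to response | Unrelated to response | 15% / 15% | 34.7 | -0.1 |
| Poor responders | Poor responders | 15% / 15% | 34.4 | -0.4 |
| Poor responders | Poor responders | 10% / 30% | 29.5 | -5.3 |
| Unrelated to response | Poor responders | 10% / 30% | 27.0 | -7.8 |
| Poor responders | Poor responders | 30% / 10% | 39.3 | +4.5 |
| Poor responders | Unrelated to response | 20% / 10% | 39.5 | +4.7 |
| Good responders | Unrelated to response | 20% / 10% | 28.8 | -6.0 |
| Good responders | Poor responders | 20% / 20% | 23.4 | -11.4 |
| Poor responders | Good responders | 20% / 10% | 42.5 | +7.7 |

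The sign depends on who leaves which arm.

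**3. What a longitudinal model recovers.** Assumptions on PGA: SD 25 mm, adjacent-visit correlation 0.85, true difference about 15 mm, dropout depending on the previous score. The first four rows are averages over 1,500 simulated trials with 17 per arm, in all of which poor responders leave. The last four used 400,000 patients per arm.

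| Pattern | Dropout active / saline | Full data | Complete case | Repeated-measures likelihood |
|---|---|---|---|---|
| Poor responders leave | 5% / 9% | 14.9 | 14.0 | 14.9 |
| Poor responders leave | 9% / 14% | 15.1 | 14.0 | 15.1 |
| Poor responders leave | 12% / 19% | 15.2 | 13.7 | 15.3 |
| Poor responders leave | 16% / 24% | 14.5 | 12.7 | 14.5 |
| Poor responders leave, same rule in both arms | 14% / 19% | 15.1 | 14.4 | 15.0 |
| Poor responders leave, mainly active | 25% / 8% | 15.0 | 17.1 | 15.0 |
| Good leave active, poor leave saline | 12% / 16% | 15.1 | 11.4 | 15.1 |
| Unrelated to response | 17% / 17% | 14.9 | 14.8 | 14.8 |

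Complete-case error runs from 11.4 - 15.1 = -3.7 mm to 17.1 - 15.0 = +2.1 mm. The likelihood estimate stays within 0.1 mm.

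**4. Size against sampling error.** With SD 25 mm and 17 per arm, the standard error of one pairwise difference is 25 × √(2/17) = 8.6 mm. For all active arms (51 patients) against saline it is 25 × √(1/17 + 1/51) = 7.0 mm. In the first four rows of step 3 the error runs from 0.9 mm (14.9 - 14.0) to 1.8 mm (14.5 - 12.7). That is 0.9/8.6 = 0.10 to 1.8/7.0 = 0.26 standard errors. On the step 2 scale the pairwise standard error is 40 × √(2/17) = 13.7 points. The patterns with 10% against 30% dropout among poor responders give 5.3/13.7 = 0.39 and 4.5/13.7 = 0.33. The two extremes give 11.4/13.7 = 0.83 and 7.7/13.7 = 0.56.

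**The case against.** **Exclusion is not written in the plan.** The plan states ITT and collects SALT and PGA at early termination, and it does not say that each week is tested separately. This stands: excluding the patient is the default behaviour of the named method, not a stated rule. It does not close the gap, because nothing tells the analyst to use an exit value or how. Reading the method as a classical repeated-measures ANOVA would not help either, since that also needs complete records.

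**A reader might infer that the IL TAC effect will be understated.** That needs poor responders to leave saline more than active treatment. The documents give no dropout rate, reason or pattern by arm. They also offer a reason for poor responders to stay: optional open-label treatment comes only after non-response at week 24. Loss of poor responders mainly from active arms reverses the sign. The stronger reading is not supported.

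**The simulations favour the proposed model.** This is fair. The data are normal and dropout depends only on observed scores, which are the conditions under which the model is unbiased. The 0.1 mm agreement shows that it works there, not that those conditions hold here. Hence the sensitivity analysis in the fix.

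**The effect is small, on secondary outcomes, in a self-described pilot.** This stands and limits the priority. Likewise, omitting week 16 from the endpoint lists does not in itself bias a week-24 ANOVA, and Bonferroni correction is already planned.

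**Conclusion.** The concern holds in a limited form. ANOVA is the only method named for continuous secondary outcomes, missing values have no rule, and ITT is therefore undefined for a patient without a week-24 assessment. The likely default excludes that patient and ignores up to five earlier visits (weeks 4 to 20).

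The resulting error has unknown sign and size. Under the assumed values it is near zero when dropout is unrelated to response or alike across arms. In most other patterns tried it is a modest fraction of a standard error, and it stayed below one standard error even in the extreme patterns. All of this rests on an assumed SD, correlation, effect and dropout, none of which the documents supply. The primary endpoint is not touched. Priority: optional to moderate, justified mainly because the better analysis uses data already being collected.

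**What to change.** In the Data Analysis Plan, for continuous outcomes up to week 24:

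- Replace the ANOVAs by one mixed model for repeated measures per outcome, with arm, visit, arm-by-visit and baseline value, unstructured covariance and a small-sample degrees-of-freedom correction. Use every on-treatment visit, including week 16. For quality of life, use weeks 12 and 24.
- Six visits mean 6 × 7 / 2 = 21 covariance parameters from 68 patients, so name a simpler structure in advance in case the model does not converge.
- Report the week-12 and week-24 contrasts, with the Bonferroni-adjusted pairwise comparisons already planned.
- Keep percent regrowth as the SALT endpoint. Absolute SALT change may be added if labelled as such.
- Assign early-termination values to the nearest scheduled visit.
- Add one sensitivity analysis under a missing-not-at-random assumption.
- Make the two lists of SALT time points agree.

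The cost is a few sentences and slightly more programming, with no new visits or patients. The model assumes that missingness depends only on observed data, which is a weaker requirement than that of a complete-case ANOVA. Weeks 36 and 48 are outside this fix, because non-responders need not be followed after week 24 or may receive open-label treatment.

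### Optional, low severity: Holm's step-down rule in place of plain Bonferroni for the follow-up pairwise comparisons would keep the same nominal 5% family-wise guarantee, lose no rejection and sometimes add one

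*Combined protocol and SAP*

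**What the plan says.** The Data Analysis Plan makes one overall test primary: "The primary analysis will be a comparison of response rates in the 4 study groups, using a chi-squared test of proportions". Follow-up is conditional on it: "If the 4-group comparison is significant, we will compare the efficacy and safety profiles of the three doses of intralesional triamcinolone head to head". Binary secondary outcomes follow the same strategy. For continuous secondary outcomes, "we will conduct 4-group ANOVA tests, followed by pairwise" comparisons where needed. The adjustment is then given in one line: "In both cases, Bonferroni correction will be made to adjust for multiple testing".

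No step-down procedure is named, so the ordinary reading is one fixed divisor for every comparison. The plan does not give the number of comparisons. It does not say whether the family is formed within an endpoint and visit or across them, and it does not name the pairwise test for binary outcomes.

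The Sample size section powers only the 4-group test. It takes "a 50% response rate for active drug (IL TAC 2.5mg/ml, 5mg/ml or 10mg/ml") against a "presumed spontaneous remission response rate of 10% for patients receiving inactive IL saline", so it assumes no difference between doses.

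**The concern.** Plain Bonferroni holds every comparison in the family to the strictest threshold, even after some have been rejected. A step-down rule relaxes the threshold after each rejection and keeps the same family-wise guarantee. Specific Aim 1 sets the three strengths against each other and against saline, and 17 patients per arm leave little power for any single pair. A rule that can only add rejections, under the same nominal guarantee and for one sentence of text, is worth considering. What is at stake is some power for the second and later pairwise findings. The primary 4-group test is not affected.

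**Working it through.** **1. The plan's own figure.** For the 4-group chi-squared test (3 df, alpha 0.05) the noncentrality is N × w². At N = 68 and w = 0.4 this is 68 × 0.16 = 10.88, giving 79.9% power. At w = 0.5 it is 68 × 0.25 = 17.0, giving 94.8%. Both agree with the stated 80% and 95%. Whether 10% against 50/50/50% really amounts to w = 0.4 is a separate question and does not touch the comparison of adjustment rules.

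**2. Thresholds.** These assume that the family is the pairs within one endpoint and time point.
- Three dose pairs. Bonferroni: 0.05/3 = 0.0167 for each. Holm, smallest p-value first: 0.0167, 0.05/2 = 0.025, 0.05.
- All six pairs. Bonferroni: 0.05/6 = 0.0083 for each. Holm: 0.05/6, 0.05/5, 0.05/4, 0.05/3, 0.05/2, 0.05.

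**3. Why nothing is lost.** Every Holm threshold is at least 0.05/m, so any p-value that passes Bonferroni passes Holm. If m0 of the m null hypotheses are true, the first true one to be rejected is reached no later than step m − m0 + 1, where the threshold is at most 0.05/m0. A false rejection therefore needs the smallest of m0 true-null p-values to be at or below 0.05/m0. That has probability at most 0.05 under any dependence, given valid p-values. The first step is the same in both rules, so Holm gains only after one comparison has already passed 0.05/m.

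**4. Binary outcome, three dose pairs.** From the documents: 17 per arm, saline 10%, 4-group gate at 5%. Assumed: Pearson chi-squared tests for pairs, and all unequal dose rates. Results are by simulation. Shaffer's rule (divisors 3, 1, 1) is shown for comparison.

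| Assumed dose rates | Quantity | Bonferroni | Holm | Shaffer |
|---|---|---|---|---|
| 25/50/75% | at least one true difference found | 81% | 81% | 81% |
| 25/50/75% | at least two | 39% | 43% | 59% |
| 30/50/70% | at least one | 60% | 60% | 60% |
| 30/50/70% | at least two | 23% | 25% | 38% |

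At 30/50/70% the power per adjacent dose pair goes from 13.6% to about 15% with Holm. At 40/50/60% the mean number of rejections goes only from 0.238 to 0.242. Larger gains need wide spreads: at 10/50/90%, 63% to 74% per adjacent pair.

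**5. Continuous outcome, six pairs.** Assumed: each dose 1.0 SD better than saline, doses equal, 17 per arm, ANOVA gate at 5%. Power per saline-dose pair is about 58% with Bonferroni, 61% with Holm and 66% with Shaffer (3, 3, 3, 3, 2, 1). Power for all three saline-dose pairs is 34%, 40% and 45%.

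**6. Actual family error, binary, three dose pairs.**

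| Dose rates | Bonferroni | Holm | Shaffer |
|---|---|---|---|
| 30/30/70% | 2.0% | 3.1% | 4.4% |
| 50/50/90% | 2.4% | 3.2% | 5.6% |
| 50/50/50% | 6.2% | 6.2% | 6.2% |

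In the last row all rules exceed 5% equally. That comes from the large-sample chi-squared test at 17 per arm, not from the step-down.

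**7. What mainly limits power.** Normal-approximation power for one pair is Φ[(|d| − z × SE0)/SE1], where d is the difference in rates, z the two-sided critical value, SE0 the pooled and SE1 the unpooled standard error. For 50% v 70% it gives 21.6% at 0.05, 14.1% at 0.025 and 10.9% at 0.0167. For 30% v 70% it gives 65.8%, 54.0% and 47.3%. The formula runs below the simulation (55.3% for 30% v 70% under Bonferroni in the 30/50/70% case), so it serves only to compare thresholds. Even with no correction, a 20-point dose difference would usually be missed.

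**The case against.** Bonferroni is valid, conventional and prespecified, and these are follow-up tests. Several points on its side stand.

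- **It does buy something.** A reader might infer that step-down is free because the nominal guarantee is the same. The second and third steps spend error that Bonferroni leaves unspent: 2.0% becomes 3.1% under Holm at 30/30/70%. Bonferroni also has simple simultaneous intervals that match its tests, which suits the Sample size section's stated aim of quantifying the effect of each dose. Holm has no equally simple counterpart. The plan does not, however, say that it will report simultaneous intervals.
- **Missed dose differences are not shown by the documents.** The plan puts all doses at 50%. Under that assumption any rejected dose pair is a false positive (mean rejections 0.073 with Bonferroni, 0.074 with Holm). Every unequal-dose figure here is an assumption. The continuous example does keep the doses equal, and its gain falls on dose versus saline.
- **The family is undefined.** The list under Study outcomes has seven secondary outcomes, most at several visits. Any rule needs the family stated, and this gap matters at least as much as the choice of rule.

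The opposite pull is towards Shaffer's divisors, which gain more. Their logic uses the restrictions among pairs within one endpoint, so they do not control a family that spans endpoints or visits. With Pearson tests at 17 per arm their actual error can reach about 5.6%, where Holm stays near 3.2%.

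**Conclusion.** The point holds as an optional efficiency suggestion of low severity. Holm keeps every Bonferroni rejection under the same nominal 5% guarantee. Under the assumed rates it raises the chance of at least two true dose findings by 4 points (39% to 43%) or 2 points (23% to 25%), and leaves the chance of at least one unchanged. In the six-pair continuous case it adds about 3 points per saline-dose pair and 6 points for all three.

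A reader might infer that the plan is in error, or that real dose differences will be missed for no benefit. The documents support neither. The correction is valid, they posit no dose difference, arm size is the main limit on power, and Bonferroni gives matching intervals and lower actual error in some configurations.

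The sizes rest on 17 evaluable patients per arm, saline at 10%, Pearson pairwise tests for binary outcomes, and families of three and six pairs.

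**What to change.** Replace the Bonferroni sentence in the Data Analysis Plan with wording such as:

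> After a significant 4-group test, pairwise p-values within each endpoint and time point are adjusted by Holm's step-down method (three dose pairs for binary outcomes, six pairs for continuous outcomes).

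This also states the family. If the sponsor meant the correction to span endpoints or visits, the sentence must say so and the number of tests must follow.

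If the sponsor prefers Shaffer's divisors (3, 1, 1; or 3, 3, 3, 3, 2, 1), they should be confined to one endpoint and time point. For binary outcomes they should be paired with an exact or otherwise size-controlled pairwise test.

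Label any ordinary 95% intervals shown beside the adjusted p-values as unadjusted, since the two can disagree. The cost is one sentence and a few lines of code, with no extra patients. The change should be made before anyone sees unblinded results, including those of the 3-month interim analysis.
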